### 7.1.3 Screening (Visit 1)

Screening evaluations may be conducted over the course of up to 3 days.

To minimize travel requirements in this patient population, manufacturing biopsies can be collected before the subject leaves the clinic on the last day of the screening visit if the subject meets all of the entry criteria for which results are available and has a clinical RDEB diagnosis. It is possible that the following results will not be available at the time that the manufacturing biopsies are taken:

- Diagnosis of RDEB by Immunofluorescence (IF)
- Diagnosis of RDEB by Electron microscopy (EM/IEM)
- Diagnosis of RDEB by Confirmation of RDEB C7 mutations in the subject
- Infectious disease panel (HIV, hepatitis B, hepatitis C) results
- NC1 status
- NC2 status

If manufacturing biopsies are not taken at the Screening visit, they may be taken at Wound Monitoring Visit 1.

The following evaluations are conducted as part of the screening visit:

- Review and signing of informed consent/assent.
- Collection of demographic data (e.g. sex, age, race, and ethnicity)
- Inclusion/exclusion criteria
- Medical history including respiratory, cardiovascular, renal, gastrointestinal, hepatic, endocrine, hematological, neurological, psychiatric and other diseases.
- Medication history
- Physical and Skin Exam
- Vital signs: blood pressure, heart rate, respiratory rate, temperature
- Collection of blood (approximately 22.5 mL) for clinical laboratory tests:
  - Serum chemistry
  - Hematology
  - HIV, Hep B, Hep C
  - RCL (this baseline blood sample may be collected at a wound monitoring visit. Results must be available prior to Day 0)
  - C7 antibody assay
- Collection of urine for pregnancy test, if applicable
- Digital imaging of wounds

CONFIDENTIAL Page 29 of 75

Final Version 8.0, 29 Oct 2019

- Identification of potential target wounds and labeling the selected wounds with sequential number of P01 through Pnn.
- Collection of one set of three (3) 3-4 mm biopsies for the manufacturing of FCX-007
- The following evaluations are required only if RDEB diagnosis documentation is not available to support entry into this protocol:
  - Collection of biopsy for EM/IEM
  - Collection of biopsy for IF and DIF
  - Collection of blood for genetic testing and determination of NC1 status
- Once all screening data is available, the PI will complete screening assessment. The subject will not be scheduled for or receive treatment until the Investigator confirms all inclusion/exclusion criteria have been met. If screening tests results received after manufacturing biopsies have been taken show the subject does not meet study criteria, the subject will be withdrawn and all material obtained for manufacturing will be destroyed unless consent has been obtained to use the tissue for future research.

# 7.2 Wound Monitoring Period

The Wound Monitoring Period may consist of 2 or more visits during the 4-month period in which FCX-007 is being manufactured. The purpose of the visits is to image potential target wounds. Potential target wounds will also undergo a skin examination during these visits. The overall length of the Wound Monitoring Period may vary due to manufacturing or data analysis. The first visit may be scheduled at least 30 days after the Screening visit and subsequent visits may be scheduled at least 30 days apart. If possible, the last wound monitoring visit may occur no more than 60 days prior to the injection of FCX-007.

Because the length of the manufacturing period may vary, the wound monitoring visits should be based on the best available estimates of when the first injection will be available.

If insufficient cell growth occurs and FCX-007 cannot be manufactured, subjects will be asked for additional manufacturing biopsies.

Collection of blood for RCL analysis can be obtained at a wound monitoring visit if not taken at screening. Results must be available prior to Day 0.

Manufacturing biopsies can be taken at Wound Monitoring Visit 1 if not obtained at the Screening Visit.

CONFIDENTIAL Page 30 of 75

Final Version 8.0, 29 Oct 2019

# 7.3 Visits 2 through 10

Study procedures are scheduled at Visits 2 (Day -2), 3 (Day 0), 4 (Day 2), 5 (Week 4), 6 (Week 12), 7 (Week 16), 8 (Week 25), 9 (Week 32), and 10 (Week 52). The Investigator may extend the subject's stay for any visit at his/her discretion based on any adverse events experienced.

Unscheduled procedures may occur during this period and resulting data should be captured on Unscheduled Visit case report forms. If deemed necessary, Investigators may attend to the subject at the hotel to check on their progress. Nursing support for bandage changes will be provided as needed.

### 7.3.1 Visit 2 (Wound Selection/Run-In)

Visit 2 procedures may occur up to 2 days (±1 day) prior to the day of FCX-007 administration. The following procedures will be performed during Visit 2:

- Re-evaluation of inclusion/exclusion criteria
- Review of medical and medication history
- Skin Exam
- Vital signs: blood pressure, heart rate, respiratory rate, temperature
- Collection of blood (approximately 12.5 mL) for laboratory tests
  - Serum chemistry
  - Hematology
- Collection of urine for pregnancy test, if applicable
- Bacterial culturing of target wounds
- Final target wound selections of up to 3 pairs from the selected potential target wounds (See Section **9.1** for details)
- Label the selected target wound pairs as T1A and T1B for the 1st pair, T2A and T2B for the 2nd pair, and T3A and T3B for the 3rd pair.
- Digital imaging of wounds.

### 7.3.2 Visit 3 (Day 0; Day of Injection)

Visit 3 procedures are scheduled to occur on the day of receipt of FCX-007. The following procedures will be performed during this visit:

- Re-evaluation of inclusion/exclusion criteria
- Review of medical and medication history
- Physical and Skin Exam
- Vital signs: blood pressure, heart rate, respiratory rate, temperature
- Bacterial culturing of target wounds (may be done if clinical evaluation is

CONFIDENTIAL Page 31 of 75

indicative of infection)

- Surgical marking around the target wounds and on the intact skin
- Digital imaging of injection sites
- Tattoos will be placed on non-blistered skin near the target wounds for the purpose of calibrating the post-dose imaging.
- Tattoos will also be placed next to the intact skin injection sites for the purpose of precisely locating the biopsy sites at follow-up visits.
- Randomly assign each wound of a target wound pair to either active treatment or control (Visit 3 only).
- Biopsy collection to be used as IF/DIF and IEM.
  - Biopsy location markings must be imaged prior to collection.
  - Biopsy collection must occur prior to administration
- FCX-007 administration to target wounds
- FCX-007 administration to the intact skin.
- Post-dose digital imaging
- Post-dose assessment of concomitant medications and adverse events

As noted above, the subject may remain at the Investigative Site or in a nearby hotel for up to 2 days following FCX-007 administration. During this period, the subject will be monitored for autoimmune reactions to FCX-007. At a minimum, subjects will be contacted once per day on days in which there are no scheduled procedures.

### 7.3.3 Visit 4 (Day 2)

Visit 4 procedures are scheduled to occur up to 2 days (±1 day) after Visit 3. The following procedures will be performed during this visit:

- Assessment of adverse events
- Assessment of concomitant medications
- Skin Exam
- Vital signs: blood pressure, heart rate, respiratory rate, temperature
- Digital imaging of wounds

Following Visit 4, the subject may return home.

CONFIDENTIAL Page 32 of 75

Final Version 8.0, 29 Oct 2019

### 7.3.4 Visit 5 (Week 4)

The visit window for the Week 4 visit is ±2 days. The following procedures will be performed during this visit:

- Assessment of adverse events
- Assessment of concomitant medications
- Skin exam
- Vital signs: blood pressure, heart rate, respiratory rate, temperature
- Collection of blood (approximately 19 mL) for laboratory tests:
  - Serum chemistry
  - Hematology
  - Analysis for C7 antibodies
  - RCL analysis
- Digital imaging of wounds
- Investigator Assessment of Wound Healing.
- Bacterial culturing of target wounds (may be done if clinical evaluation is indicative of infection).
- Skin biopsies will be collected for IEM, genomic DNA/mRNA and/or IF/DIF evaluation at the site of Investigational Product/placebo administration as outlined in **Table 2**. Biopsy location markings must be imaged prior to collection.
- Skin biopsies will be collected from intact skin administration sites for IEM, genomic DNA/mRNA and/or IF/DIF evaluation as outlined in **Table 2**.
- Surgical marking around the target wounds and on the intact skin
- Tattoos will be placed on non-blistered skin near the target wounds for the purpose of calibrating the post-dose imaging.
- Tattoos will also be placed next to the intact skin injection sites for the purpose of precisely locating the biopsy sites at follow-up visits.
- FCX-007 administration to target wounds
- FCX-007 administration to the intact skin.
- Post-dose digital imaging
- Post-dose assessment of concomitant medications and adverse events

CONFIDENTIAL Page 33 of 75

Final Version 8.0, 29 Oct 2019

### 7.3.5 Visit 6 (Week 12)

The visit window for Week 12 is ±1 week. The following procedures will be performed during these visits:

- Re-evaluation of inclusion/exclusion criteria
- Review of medical history
- Assessment of adverse events
- Assessment of concomitant medications
- Physical and Skin exam
- Vital signs: blood pressure, heart rate, respiratory rate, temperature
- Collection of blood (approximately 19 mL) for laboratory tests:
  - Serum chemistry
  - Hematology
  - Analysis for C7 antibodies
  - RCL analysis
- Digital imaging of wounds
- Investigator Assessment of Wound Healing.
- Bacterial culturing of target wounds (may be done if clinical evaluation is indicative of infection).
- Skin biopsies will be collected for IEM, genomic DNA/mRNA and/or IF/DIF evaluation at the site of Investigational Product/placebo administration as outlined in **Table 2**. Biopsy location markings must be imaged prior to collection.
- Skin biopsies will be collected from intact skin administration sites for IEM, genomic DNA/mRNA and/or IF/DIF evaluation as outlined in **Table 2**.

### 7.3.6 Visit 7 (Week 16)

Based on the subject's availability to travel, this visit may be performed via a telephone consult or in the office. If the visit is performed via telephone consult, the investigator and subject/guardian will review adverse events and concomitant medications. If the visit is performed in the office, the following procedures will be performed:

- Assessment of adverse events
- Assessment of concomitant medications
- Skin exam
- Vital signs: blood pressure, heart rate, respiratory rate, temperature
- Collection of blood (approximately 19 mL) for laboratory tests:
  - Serum chemistry
  - Hematology

CONFIDENTIAL Page 34 of 75

- Analysis for C7 antibodies
- RCL analysis
- Digital imaging of wounds
- Investigator Assessment of Wound Healing.
- Bacterial culturing of target wounds (may be done if clinical evaluation is indicative of infection).

### 7.3.7 Visit 8 (Week 25)

The visit window for Week 25 is ±2 weeks.

The following procedures will be performed:

- Assessment of adverse events
- Assessment of concomitant medications
- Skin exam
- Vital signs: blood pressure, heart rate, respiratory rate, temperature
- Collection of blood (approximately 19 mL) for laboratory tests:
  - Serum chemistry
  - Hematology
  - · Analysis for C7 antibodies
  - RCL analysis
- Digital imaging of wounds
- Investigator Assessment of Wound Healing.
- Bacterial culturing of target wounds (may be done if clinical evaluation is indicative of infection)
- Skin biopsies will be collected for IEM, genomic DNA/mRNA and/or IF/DIF as outlined in **Table 2**. Biopsy location markings must be imaged prior to collection.
- Skin biopsies will be collected from intact skin administration sites for IEM, genomic DNA/mRNA and/or IF/DIF evaluation as outlined in **Table 2**.

### 7.3.8 Visit 9 (Week 32)

Based on the subject's availability to travel, this visit may be performed via a telephone consult or in the office. If the visit is performed via telephone consult, the investigator and subject/guardian will review adverse events and concomitant medications. If the visit is performed in the office, the following procedures will be performed:

- Assessment of adverse events
- Assessment of concomitant medications
- Skin exam
- Vital signs: blood pressure, heart rate, respiratory rate, temperature

CONFIDENTIAL Page 35 of 75

- Collection of blood (approximately 19 mL) for laboratory tests:
  - Serum chemistry
  - Hematology
  - Analysis for C7 antibodies
  - RCL analysis
- Digital imaging of wounds
- Investigator Assessment of Wound Healing.
- Bacterial culturing of target wounds (may be done if clinical evaluation is indicative of infection).

### 7.3.9 Visit 10 (Week 52) / Early Termination (ET)

Week 52 is the final visit of the Treatment Period. The visit window for Week 52 is ±2 weeks. The procedures below are the same to be performed for subjects who terminate early from the study. If a subject refuses or is unable to return for an Early Termination Visit, a local physician may be requested to evaluate the subject. At least 3 documented attempts should be made to contact subjects prior to making a determination of lost to follow-up.

- Assessment of adverse events
- Assessment of concomitant medications
- Physical and skin exam
- Vital signs: blood pressure, heart rate, respiratory rate, temperature
- Collection of blood (approximately 19 mL) for laboratory tests:
  - Serum chemistry
  - Hematology
  - Analysis for C7 antibodies
  - RCL analysis
- Digital imaging
- Investigator Assessment of Wound Healing.
- Bacterial culturing of target wounds (may be done if clinical evaluation is indicative of infection).
- Skin biopsies will be collected for IEM, genomic DNA/mRNA and/or IF/DIF evaluation at the site of Investigational Product/placebo administration as outlined in Table 2.
- Skin biopsies will be collected from intact skin administration sites for IEM, genomic DNA/mRNA and/or IF/DIF evaluation as outlined in **Table 2**.

CONFIDENTIAL Page 36 of 75

Final Version 8.0, 29 Oct 2019

#### 7.4 Unscheduled Visits

Unscheduled procedures will be conducted at the discretion of the Investigator. Procedures may include, but are not limited to physical exam, photographs, skin assessment, investigator assessment of wound healing, skin biopsies, wound cultures, and/or blood draws for lab procedures.

## 7.5 Long-Term Follow-Up Period

Upon completion of the End of Study / Early Termination Visit, subjects will enter into the Long-Term Follow-Up Period.

#### 7.5.1 Years 1 - 5

At a minimum, subjects will be contacted yearly for at least 5 years. Subjects will be contacted by phone. In addition, the subject's primary care provider will be asked to contact the Investigator regarding any unexpected or serious adverse events. Telephone contact reports will document the discussions and the information obtained will be captured on case report forms. The following activities will occur at the one-year follow-up intervals:

- Collection and analysis of blood sample for RCL testing (can be done remotely).
  - If all post-treatment assays are negative during the first year (e.g., Weeks 4, 12, 16, 25, 32, and 52), collection of the yearly follow-up samples will be discontinued.
- Recording of exposures to mutagenic agents and other medicinal products
- Recording of any new serious adverse events, hospitalizations, or illnesses (including new malignancies, new incidence or exacerbation of a pre-existing neurologic disorder, new incidence or exacerbation of a prior rheumatologic or other autoimmune disorder, new incidence of a hematologic disorder).
- Discussion with primary care provider regarding medication and medical history.
- If a skin cancer occurs in the region of the FCX-007 administration, attempts will be made to collect samples of the skin cancer to evaluate cells for the presence of viral vector.

#### 7.5.2 Years 6 - 15

Subjects will continue to be followed-up on an annual basis for at least 15 years following FCX-007 administration. Follow-ups from years 6 to 15 include:

- Collection and analysis of blood sample for RCL testing (can be done remotely).
  - If all post-treatment assays are negative during the first year (e.g., Weeks 4, 12, 16, 25, 32, and 52), collection of the yearly follow-up samples will be discontinued.

CONFIDENTIAL Page 37 of 75

FI-EB-001 RDEB Phase I/II Protocol

Final Version 8.0, 29 Oct 2019

- Recording of exposures to mutagenic agents and other medicinal products
- Recording of any new adverse events, hospitalizations, or illnesses (including new malignancies, new incidence or exacerbation of a pre-existing neurologic disorder, new incidence or exacerbation of a prior rheumatologic or other autoimmune disorder, new incidence of a hematologic disorder).
- Discussion with primary care provider regarding medication and medical history.

CONFIDENTIAL Page 38 of 75

Final Version 8.0, 29 Oct 2019

## 8 Procedures: FCX-007 Administration to Intact Skin

#### 8.1 Skin Selection

Select an area of intact, non-blistered skin. The skin should have the following characteristics:

- It should be an area free of blisters, wounds or contracture tissue as assessed by the Principal Investigator during the Wound Monitoring Period.
- There should be no sign of recent blistering at the time of injection.
- The neck, face, head, groin, hands, feet, joints, and axilla are excluded areas.
- Per the Investigator's judgement, select an area of the body with a minimal likelihood of blistering throughout the trial.

[figure not shown]
#### 8.2 Determination of the Number of Administrations

FCX-007 will be administered to at least 6 and up to 12 intact skin injection sites. It will only be possible to administer FCX-007 to more than 6 sites if less than 54 injections are administered to the target wound(s).

## 8.3 Skin Markings

At Visit 3 (Day 0) and Visit 5 (Week 4), use a surgical marker to place dots on the skin 1 cm apart in a linear array. Place tattoos so that the ends of the administration rows can be identified (**Figure 3**) at future visits.

Figure 3 - Intact Skin Grid

CONFIDENTIAL Page 39 of 75

Fibrocell Technologies RDEB Phase I/II Protocol Final Version 8.0, 29 Oct 2019

## 8.4 Imaging

The intact skin grid will be imaged at baseline after the skin markings have been applied. This image will be used as a reference for biopsies at follow-up visits. The images will be captured by a Canfield VECTRA H1XP (the "Canfield").

#### 8.5 FCX-007 Administration to Intact Skin

On Visit 3 (Day 0) and Visit 5 (Week 4), intradermally administer at least 6 0.25 mL injections of FCX-007 to the intact skin per the administration instructions in **Appendix A:Investigational Product Administration Instructions**.

CONFIDENTIAL Page 40 of 75

Final Version 8.0, 29 Oct 2019

## 9 Procedures: FCX-007 Administration to Wound(s)

#### 9.1 Selection

A preliminary evaluation of target wounds will occur at the Screening Visit. Potential wounds that meet criteria will be identified at Screening and followed throughout the Wound Monitoring Period. New wounds may also be identified during the Wound Monitoring Period. Final target wound and wound pair selection will occur on Visit 2 based on meeting the following criteria:

- 1. The total injection area (circumference plus the lengths of the axes) is a maximum of approximately 54 linear cm (see **Figure 4** for more details).
- 2. If more than one pair of wounds is identified, the sum of the injection areas a maximum of approximately 54 linear cm.
- 3. If multiple pairs of wounds are identified that meet criteria, wounds with the most consistent wound areas throughout the Wound Monitoring Period are to be selected for the study.

If no wound meets criteria 1 and 2 above, a smaller region of a larger wound may be selected for treatment if it can be matched to a similar area of a larger wound as the control. When selecting a smaller region appropriate for treatment, every effort should be made to minimize the border between the treated and the untreated regions of the wound (See **Figure 6B**). Ideally, a narrow peninsula off the main portion of the wound should be selected for administration of FCX-007.

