### 1.2 FCX-007 Background

### 1.2.1 Cell Manufacturing

[figure not shown]
FCX-007 is an autologous cell product manufactured by *ex vivo* gene modification and expansion of dermal fibroblasts obtained from one set of three 3-4 mm biopsies of the patient's skin. The biopsies are shipped in a sterile buffer solution to a central manufacturing facility, where they are digested with enzymes to release the fibroblast cells, which are then seeded into a tissue culture vessel. The cells are expanded, transduced with INXN-2004 (a lentiviral vector encoding the functional COL7A1 gene), and expanded further to obtain a sufficient quantity for study treatment. Cells undergo Drug Substance release testing. The Drug Product for patient injection is shipped same day or overnight prior to each scheduled day of investigational treatment. FCX-007 Drug Substance is evaluated against Drug Product release specifications. FCX-007 Drug Product is shipped refrigerated for overnight delivery to the clinic and is to be administered prior to the expiration date and time indicated on the product label. FCX-007 cells are injected intradermally at the periphery of RDEB wounds as well as into intact skin.

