#### 9.1.2 Pairing and Labeling of Selected Wound Pairs

Potential target wounds will be identified by a continuous sequential numbering of Pair 01 (P01) through Pnn. Depending on the size of the largest wound in the pair, the investigator may select up to three pairs of wounds for inclusion in the study. Because the Investigator will not know which of the two paired wounds will be randomly assigned to receive FCX-007, it should be assumed that the largest of the two wounds will receive FCX-007 when calculations are made to determine

CONFIDENTIAL Page 41 of 75

[figure not shown]
Phase I/II Protocol Final Version 8.0, 29 Oct 2019

how many wound pairs to select. The final selected target wound pairs will be labeled as T1A and T1B for the 1st pair, T2A and T2B for the 2nd pair, and T3A and T3B for the 3rd pair.

The pairs should be ordered from smallest to largest; T1A and T1B will have the smallest injection area, T2A and T2B will have the next smallest injection area, etc. On the day of administration, the smallest wounds will be injected first, the second smallest second, etc.

**Figure 4** provides an example and sample calculations for a subject in which two pairs of wounds are selected for inclusion in the study. As shown in the example below, if more than one pair of wounds is identified, the sum of the injectable areas of the largest wounds in the pair must be less than or equal to 54 linear cm. Wounds should be selected with the intent to administer investigational product to the entire injectable area of the target wounds.

Figure 4 - Wound Pairing and Selection Calculations Example

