#### 9.4 FCX-007 Administration

#### 9.4.1 Preparation

A surgical marker will be used to make the following marks:

- Dots at the injection sites around the periphery of the wound at 1 cm intervals
- Two lines, 1 cm apart, perpendicular from the wound margin, indicating the path of injections across the axes.
- Two circles indicating the location of the IF/DIF and IEM biopsies

CONFIDENTIAL Page 43 of 75

[figure not shown]
Fibrocell Technologies RDEB Phase I/II Prote

Final Version 8.0, 29 Oct 2019

**Figure 5** provides a diagram of a target wound with markings. After the markings are in place, the wound will be imaged and biopsies obtained.

Prior to the first administration of IP, small tattoos will be placed on non-blistered skin near target wounds for the purpose of calibrating the images. Topical anesthetic cream will be removed from the treatment area prior to treatment. The treatment area will be cleansed with antiseptic solution.

Figure 5 – Sample Drug Administration Preparation Wound Markings

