#### 9.4.2 Administration

Reference Appendix A: Investigational Product Administration Instructions for detailed instructions regarding the administration of investigational product.

Investigational product is administered intradermally at 1 cm intervals around the periphery of target wounds. The intradermal administration must occur up to 1.0 cm of the wound margin and be administered into the mid-to-superficial dermis. Investigators are to administer 0.25 mL per injection. **Figure 6** provides a graphical depiction of an example target wound showing injection sites and biopsy locations. Locations are shown for (A) treatment of an entire wound, and (B) treatment of a region of a large wound.

[figure not shown]
CONFIDENTIAL Page 44 of 75

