# Appendix A: Investigational Product Administration Instructions

- 1. Intradermal injections are to be administered by the Investigator or an appropriately trained delegated health care professional.
- 2. Administer anesthesia. Subjects will be administered anesthesia per standard of care at the Investigative Site. To minimize pain and discomfort during the investigational product administration, the Investigator should determine the most appropriate anesthetic for each subject, including the use of topical anesthetic cream, local anesthesia, conscious (moderate) sedation, general anesthesia (if undergoing another procedure at time of injection) or a combination thereof. In addition, medication should be considered during and after the injections to treat pain and/or anxiety (i.e. lorazepam).
- 3. Mark the skin as indicated in Section 8.2 (intact skin) and Section 9.4.1 (wounds).
- 4. Approximately 15 minutes prior to the administration of FCX-007, remove the subject's treatment vials from the shipper.
- 5. Resuspend the cells by gently inverting the injection vial three times.
- 6. Tap the top of each vial to release any fluid in the cap prior to opening the vials. Do not dilute the product.
- 7. Unscrew the cap and, using a detachable bore (21-gauge needle), aseptically draw 1.0 mL from one vial.
- 8. Once the product is in the syringe, remove the 21-gauge needle and replace it with the 30-gauge needle for injection of the product. Do not use a 21-gauge needle for injection of the product. Follow sterile technique during this process. Note: Living cells are fragile and should be handled gently, especially when being aspirated into a syringe. Go slowly and use care during this process.
- 9. Hold the syringe using the proper technique: the bevel facing upwards and the arms of the syringe are vertical. Some clinicians may prefer to bend the needle upwards at about a 15-degree angle to facilitate staying in a superficial plane but use of this technique is optional. Grip the syringe with the middle and index finger below the arms, placing the thumb on the upper arm. Do not place the thumb on the plunger while directing the needle into the skin to avoid premature discharge of the product.
- 10. Insert the 30-gauge needle at the first mark.

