- 11. Introduce the needle into the superficial papillary dermis at 0.25 mL per linear centimeter and bring the needle along a line parallel to the wound margin. The shadow of the needle under the skin must be visible if the injector is in the correct plane. If it is not, replace the needle just adjacent to the initial area of insertion in a more superficial plane.

CONFIDENTIAL Page 72 of 75

- 12. The graduated markings on the syringe should be visible to ensure that the correct amount is being injected.
- 13. Once the needle is inserted, apply light pressure to the plunger and inject very slowly, injecting very tiny boluses into the treatment area as the needle is withdrawn (the cells must be injected as delicately as possible). Keep a close eye on the amount and the skin to ensure only 0.25 mL is injected into each centimeter, and a wheal is formed with each bolus. Stop injecting before withdrawing the needle and remove your thumb from the plunger.
- 14. Immediate blanching of the skin or a small wheal must be seen as the product is injected. If the needle is in the superficial (papillary) dermis it will be difficult to inject too much volume. If you see no blanching or wheal when the product is initially injected, reposition the needle in a more superficial plane and inject additional product.
- 15. Record any seepage of product or immediate impact to overall wound size.

Figure 7 - Photographs of Intradermally Administered Fibroblasts Cells

CONFIDENTIAL Page 73 of 75

Final Version 8.0, 29 Oct 2019

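### The 54-cm wound limit counts the wound axes, but sections disagree on whether the axes are injected, so 54 + 6 = 60 injections follows directly on only one reading

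*Combined protocol and SAP*

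**What the plan says.** **Axes counted and marked for injection.** Section 9.1 gives the selection limit: "The total injection area (circumference plus the lengths of the axes) is a maximum of approximately 54 linear cm". Section 9.1.2 applies the same figure across pairs: "the sum of the injectable areas of the largest wounds in the pair must be less than or equal to 54 linear cm". It also says wounds are to be chosen with a view to treating all of that injectable area. Section 9.3 has investigators trace both perimeter and axes. Section 9.4.1 asks for dots every 1 cm round the periphery and, in addition, "Two lines, 1 cm apart, perpendicular from the wound margin, indicating the path of injections across the axes".

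**Periphery.** Section 1.2.1 says "FCX-007 cells are injected intradermally at the periphery of RDEB wounds as well as into intact skin". Section 9.4.2, the administration section, says "Investigational product is administered intradermally at 1 cm intervals around the periphery of target wounds" and adds "The intradermal administration must occur up to 1.0 cm of the wound margin". It does not mention the axes.

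**Mixed.** Appendix A step 3 refers the injector to the 9.4.1 wound marks, which include the axis paths. Step 11 then says to "bring the needle along a line parallel to the wound margin".

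**The budget.** The synopsis and section 3.1 say that wounds should come as close as possible to 54 linear cm, leaving at least 6 injections for intact skin and making 60 in total. Each injection is 0.25 mL and the maximum is 15 mL. Section 8.2 allows 6 to 12 intact-skin sites, with more than 6 only if the wounds take fewer than 54.

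**Minor point.** The synopsis entry on test product and dose has up to 20 mL manufactured for the protocol. The same entry allows up to 15 mL at Visit 3 and up to a further 15 mL at Visit 5. Section 6.2.1.1 provides up to 30 vials, each with 1.0 mL recoverable.

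**The concern.** A person who sizes wounds under 9.1 and marks them under 9.4.1 has drawn injection paths across the wound. Section 9.4.2 gives no instruction for those paths, and if its distance rule means within 1.0 cm of the margin, most of a long axis lies outside it. The 54-cm figure appears to be a count of wound injections at one per centimetre. That works only if everything counted in the 54 cm is injected.

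The primary objective is safety, there may be up to three sites, and target wounds may be treated twice. If sites follow different sections, injection location, number of injections and volume could differ for the same wound, and safety and wound-healing results would be pooled over different exposures.

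**Working it through.** **Inputs from the protocol:** 54 linear cm, circumference plus axes (9.1); injections every 1 cm round the periphery (9.4.1, 9.4.2); 0.25 mL per linear cm (Appendix A step 11) and per injection (9.4.2); 6 to 12 intact-skin sites (8.2); up to 60 injections and 15 mL (synopsis, 3.1).

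**1. The plan's own figure.** At one injection per cm over the full 54 cm: 54 + 6 = 60 injections, and 60 × 0.25 = 15 mL. It reproduces exactly if the axes are injected.

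**2. What margin-only injection would need.** With the maximum of 12 intact-skin sites, 60 − 12 = 48 wound injections. With the injection line at the margin, 48/54 = 89% of the budget would have to be margin.

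**3. Illustration.** Assumed, not in the documents: one circular wound at the limit, two axes counted, one injection per cm, line at the margin.
- Diameter: d = 54/(π + 2) = 54/5.1416 = 10.50 cm.
- Margin: π × 10.50 = 33.0 cm (61% of 54). Axes: 2 × 10.50 = 21.0 cm.

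| Pattern | Injections | Volume |
|---|---|---|
| Margin and axes, 6 intact | 33 + 21 + 6 = 60 | 15 mL |
| Margin only, 6 intact | 33 + 6 = 39 | 9.75 mL |
| Margin only, 12 intact | 33 + 12 = 45 | 11.25 mL |

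**4. Sensitivity to shape.** For ellipses with circumference plus both axes equal to 54 cm, the margin runs from 33.0 cm (circle) to 36.0 cm (flat limit, 67%). With the line at the margin, the totals are 39 to 42 injections with 6 intact-skin sites (9.75 to 10.5 mL) and 45 to 48 with 12 (11.25 to 12.0 mL).

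**5. A case that does reach 60.** Take three equal circular wounds with the injection line 1.0 cm outside the margin. The margins still sum to 33.0 cm, and the offset adds 2π cm per wound: 33.0 + 3 × 2π = 51.8 wound injections, above 48. The shortfall is therefore not universal.

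**6. Does the statement that most injections go round the margin settle it?** No. In the circle it holds either way: 33/60 = 55% with axes, 33/39 = 85% without.

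**7. The distance rule.** If 9.4.2 means within 1.0 cm of the margin, then on each 10.50-cm axis of the circle only the two end centimetres qualify, and 10.50 − 2 × 1.0 = 8.50 cm does not.

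**8. Minor point.** 15 + 15 = 30 mL and 30 vials × 1.0 mL = 30 mL, against 20 mL: a difference of 10 mL.

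**The case against.** The strongest reply is that much of the conflict is silence. Sections 1.2.1 and 9.4.2 describe the periphery, but neither says that injection is confined to it, and 1.2.1 is one background sentence. This is fair, and it narrows the sharpest contradiction to 9.4.1 against the 9.4.2 distance rule and Appendix A step 11. It does not remove it: the administration section gives no instruction for paths that the preparation section marks for injection.

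Second, Figures 4 to 6 carry the sample calculation, the markings and the injection sites, and they are not visible in the copy reviewed. They may show the intent and reduce the practical effect. The written sections would still disagree.

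Third, the Summary of Changes for version 8.0 records the removal of injection across the axes, so 9.1 and 9.4.1 may hold leftover wording. The finding does not rely on that log. If the explanation is right, the clean-up is still needed, and the 54-cm budget must be checked with it.

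Fourth, no stated total is wrong: 54 + 6 = 60 is exact, 54 cm is an approximate maximum, 60 injections and 15 mL are ceilings, and 8.2 provides for fewer than 54 wound injections. All of this stands. The fault is one of consistency: the stated route to 60 depends on a pattern that the text leaves open. It also stands that the illustration rests on assumed geometry.

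**Conclusion.** The concern holds. The current text conflicts on where product is injected at target wounds, and showing this needs no assumption about wound shape. The 60-injection budget follows directly from the 54-cm definition if the axes are injected, and does not follow from it if only the margin is.

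The size is less certain. For a single circular wound at the limit with injections on the margin, the gap is 15 to 21 injections (60 − 45 and 60 − 39), or 3.75 to 5.25 mL. An offset line, fewer axes counted, several wounds or an irregular margin shrink the gap and can close it. Neither reading exceeds the ceilings, so no breach of dose is claimed. What is at stake is uniformity of injection sites, count and volume.

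The 20 mL against 30 mL discrepancy is real but minor. Vial supply matches two administrations of 15 mL, the quantities in section 6.1.1 are redacted and Table 1 is not visible, so no effect on dosing is claimed.

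**What to change.** Reconcile the synopsis study design and sections 1.2.1, 3.1, 8.2, 9.1, 9.1.2, 9.4.1 and 9.4.2 with Appendix A steps 3 and 11, so that they describe one injection pattern, and check Figures 4 to 6 against it. Then confirm that the 54-cm limit, the 6 to 12 intact-skin sites and the 60-injection total are consistent with that pattern. The check should allow for 9.1.2, which sizes on the larger wound of each pair although the smaller one may be assigned treatment.

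Separately, reconcile the 20 mL in the synopsis with the two administrations in the same entry and with section 6.2.1.1.

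Which pattern and which volume apply is for the sponsor to state. The cost is protocol wording and a clarification to sites, with no new data or subjects.
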